6.3 Lifestyle Restrictions

6.3.1 *Exposure to Sunlight*

Every precaution needs to be taken to limit excessive sun exposure though out the duration of the study. General skin care measures are recommended that are standard for patients with CLE and SLE, as follows: use of broad spectrum sunscreen (minimum sun protection factor 30 and with inorganic ingredients (zinc oxide, titanium dioxide), avoiding sun exposure, wearing sun-protective clothing, avoidance of alcohol-based emollients, avoidance of over-the-counter anti-acne medications and alcohol-based skin care products, and avoidance of perfumed soaps and detergents, and similar measures. Participants should avoid tanning (including tanning salons), sunbathing, and outdoor activities that require prolonged or extensive sun exposure.

6.3.2 *Meals and Dietary Restrictions*

Not applicable.

6.4 Screen Failures

Screen failures are defined as participants who consent to participate in the clinical study but who are not subsequently randomized in the study/included in the analysis population. A minimal set of screen failure information is required to ensure transparent reporting of screen failure

participants, to meet the Consolidated Standards of Reporting Trials (CONSORT) publishing requirements, as applicable, and to respond to queries from regulatory authorities. Minimal information includes date of consent, demography, screen failure details, eligibility criteria, and any serious AEs.

6.4.1 Retesting During Screening Period - Rescreening

For laboratory parameters and/or assessments that initially do not meet eligibility requirements, a single retest within the 28 day screening period is permitted in an effort to find all possible well-qualified participants. Consultation with the Clinical Trial Physician/Medical Monitor may be needed to identify whether repeat testing of any particular parameter is clinically relevant.

The study permits the rescreening (after the end of the initial 4-week Screening Period) of a participant who discontinues the study as a pretreatment failure (ie, the participant fails screening or randomization and has not been treated). The participant must be re-consented and will be assigned a new identification number, and a full Screening Visit must be performed again.

A participant can be rescreened twice (ie, if the participant fails 2 rescreening attempts, no additional rescreening is allowed). Depending on the timing of rescreening, repetition of some assessments may not be required. Duration of existing treatments and required discontinuation periods shall be considered relative to the given Screening Visit and/or randomization.

Laboratory parameters and/or assessments that are included in [Table 2-1, Screening Procedural Outline](#), may be repeated in an effort to find all possible well-qualified participants. Consultation with the Clinical Trial Physician/Medical Monitor may be needed to identify whether repeat testing of any particular parameter is clinically relevant.

The most current result prior to randomization is the value by which study inclusion will be assessed, as it represents the participant's most current clinical state.

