1 SYNOPSIS

Protocol Title: A Phase 2 Randomized, Double-Blind, Placebo-Controlled Study to Evaluate Efficacy and Safety of Deucravacitinib (BMS-986165) in Participants with Active Discoid and/or Subacute Cutaneous Lupus Erythematosus (DLE/SCLE)

Brief Title: A Phase 2 Clinical Study to Assess the Safety and Efficacy of Deucravacitinib in Participants with Active DLE and/or SCLE

Study Phase: 2

Rationale:

This Phase 2 study will assess if deucravacitinib (BMS-986165) is biologically active and potentially effective in the treatment of participants with moderate to severe discoid lupus erythematosus and/or subacute cutaneous lupus erythematosus (DLE/SCLE) with or without systemic lupus erythematosus (SLE), that is inadequately controlled with standard of care therapy.

Study Population:

Male and female participants (18 to 75 years of age) must have a biopsy-confirmed clinical diagnosis of DLE/SCLE, and inadequate response, defined as therapeutic failure or intolerance to an oral corticosteroid, and/or antimalarial and/or immunosuppressant.

Key Inclusion Criteria:

- Participants must have a diagnosis of DLE/SCLE for at least 3 months prior to Screening Visit.
- Participants must meet both clinical and histopathological diagnostic cutaneous lupus erythematosus (CLE) criteria per protocol.
- Participants are required to have active moderate to severe cutaneous disease based on the Cutaneous Lupus Erythematosus Disease Area and Severity Index-Activity (CLASI-A) score ≥ 8 at Screening AND Baseline Visit (Day 1).
- Participants must currently be receiving treatment for DLE/SCLE with a stable regimen of at least one of the following medications: oral corticosteroid, and/or antimalarial, and/or immunosuppressant.

Key Exclusion Criteria:

- Participants with any of the following specific CLE subtypes in isolation: acute cutaneous lupus erythematosus (ACLE), lupus tumidus, lupus (profundus) panniculitis, chilblains.
- Participants with forms of drug-induced CLE and/or drug-induced SLE.
- Participants with active kidney disease, defined as an estimated glomerular filtration rate (eGFR) of < 60 mL/min/1.7 m² and/or proteinuria > 0.5 g/24 h (spot urine protein/creatinine ratio [UPCR]: > 56.5 mg/mmol).

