CLASI-A assessment must be performed for eligibility at Screening and Baseline (Day 1) prior to randomization for confirmation of minimally required disease activity (CLASI-A ≥ 8). Following confirmation of enrolment eligibility by the PI [REDACTED], participants will be randomized at a 1:1:1 ratio to receive:

- Deucravacitinib 3 mg BID
- Deucravacitinib 6 mg BID
- Deucravacitinib-matching Placebo BID.

Participants will be evaluated at study visits every 4 weeks through Week 16.

Active Treatment Period (Week 16 to Week 52):

Participants who complete the placebo-controlled treatment period will continue into an active treatment period for an additional 36 weeks of treatment.

At Week 16, participants receiving placebo during the placebo-controlled treatment period will be re-randomized 1:1 in a blinded-fashion to receive active treatment with either deucravacitinib 3 mg BID or 6 mg BID until Week 52. Participants receiving deucravacitinib 3 mg BID or 6 mg BID through Week 16 will continue the originally randomized treatment in a blinded manner through Week 52.

Post-Treatment Follow-up Period:

All participants will be followed for 28 days (\pm 3 days) after the last dose of study treatment for safety monitoring.

Number of Participants:

Approximately 75 participants are expected to be randomized.

Treatment Arms and Duration:

[figure not shown]
Study treatment: Participants in all treatment groups will take oral doses of investigational product (IP) for the 52-week treatment period as presented in Table 2.

Table 2: Study Treatments

Medication	Dose	IP/Non-IP
deucravacitinib BID	3 mg or 6 mg	IP
Placebo BID	Not applicable	IP

[figure not shown]
Abbreviations: BID = twice a day; IP = Investigational Product; Non-IP = Non-investigational Product.

Notes: In all treatment groups, participants will take their randomly assigned treatment twice daily. No titration or modification of IP doses is permitted.

Data Monitoring Committee:

A Data Monitoring Committee (DMC) with multi-disciplinary representation will be established to evaluate safety data (eg, AEs, laboratory parameters) on a periodic basis to ensure the ongoing safety of study participants and the overall benefit/risk for the study is maintained. The DMC responsibilities, authorities, and procedures will be documented and followed according to the DMC charter.

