FSH	X	Women only, if needed to confirm postmenopausal status. Females under the age of 55 years must have a serum follicle stimulating hormone level > 40 mIU/mL to confirm menopause.
Chemistry, Hematology, Urinalysis, and Coagulation Tests	X	Includes blood and urine samples. See Section 9.4.5 .
Spot Urine for Protein:Creatinine Ratio	X	See Section 6.2, Exclusion Criteria, 1), c) .
Tuberculosis screening	X	See Section 9.4.2 .
Serology	X	Hepatitis C antibody, anti-HBs, HBsAg, anti-HBc, HIV-1, and HIV-2 antibody.
C3, C4, Anti-dsDNA	X	
Disease Assessment		
CLASI	X	Refer to Appendix 8 .

Table 2-1: Screening Procedural Outline (IM011132)

Procedure ^a	Screening Visit (28 days) ^b	Notes

Abbreviations: anti-dsDNA =anti-double stranded deoxyribonucleic acid (antibody); anti-HBs = anti-hepatitis B surface antibody; BMI = body mass index; C3 = complement 3; C4 = complement 4; CLASI = Cutaneous Lupus Erythematosus Disease Area and Severity Index; CLE = cutaneous lupus erythematosus; DLE = discoid lupus erythematosus; [REDACTED] ECG(s) = electrocardiograms; [REDACTED] anti-HBc = hepatitis B core antibody; HBsAg = hepatitis B surface antigen; [REDACTED] HIV = human immunodeficiency virus; [REDACTED] IRT = Interactive Response Technology; PA = posterioranterior; [REDACTED] SAE = serious adverse event; SCLE = subacute cutaneous lupus erythematosus; [REDACTED] WOCBP = women of childbearing potential.

^a Additional testing or assessments may be performed as clinically necessary or where required by institutional or local regulations. Some of the safety assessments intended to be used as safety monitoring by the treating physician may not be captured as data in the CRF.

^b Screening procedures should be performed within the 28 day window prior to Day 1. If eligibility parameters cannot be obtained within this time period, the screening period may be extended by up to 7 calendar days if approved by the Clinical Trial Physician/Medical Monitor.

Table 2-2: Placebo-Controlled Treatment Period Procedural Outline Up to Week 16 (IM011132)

Procedure ^a	D1 (Baseline)	W4 D29 (±3d)	W8 D57 (±3d)	W12 D85 (±3d)	W16 D113 (±3d)	Notes:
Eligibility Assessments						
Eligibility / Randomization	X					Confirm eligibility criteria and complete Baseline assessments prior to randomization.
Re-randomized for Active Treatment Period					X	Only participants on placebo will be re-randomized, but IRT will be contacted for all participants to maintain the blind.
Safety Assessments						

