5.1.2 Placebo-controlled Treatment Period (Day 1 to Week 16)

CLASI-A assessment must be performed for eligibility at Screening and Baseline (Day 1) prior to randomization for confirmation of minimally required disease activity (CLASI-A \geq 8). Following confirmation of enrolment eligibility by the PI [REDACTED] participants will be randomized at a 1:1:1 ratio to receive:

- Deucravacitinib 3 mg BID
- Deucravacitinib 6 mg BID
- Deucravacitinib-matching Placebo BID.

Participants will be evaluated at study visits every 4 weeks through Week 16 ([Table 2-2](#)).

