6 STUDY POPULATION

Eligibility criteria for this study have been carefully considered to ensure the safety of the study participants.

All screening evaluations must be completed and reviewed to confirm that potential participants meet all eligibility criteria. The investigator will maintain a screening log to record details of all participants screened and to confirm eligibility or record reasons for screening failure, as applicable.

However, all laboratory testing must be performed by the study-specific central laboratory.

Prospective approval of protocol deviations to recruitment and enrollment criteria, also known as protocol waivers or exemptions, is not permitted.

For entry into the study, the following criteria MUST be met.

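### Does the retest rule in Section 6.4.1 undo the requirement of CLASI-A at least 8 at both Screening and Day 1?

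*Combined protocol and SAP*

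**What the plan says.** The key inclusion criteria in the Synopsis require a "CLASI-A) score ≥ 8 at Screening AND Baseline Visit (Day 1"). Section 5.1.2 gives the same two time points: "CLASI-A assessment must be performed for eligibility at Screening and Baseline (Day 1) prior to randomization", and the Synopsis gives the purpose, "for confirmation of minimally required disease activity". The matching criterion in Section 6.1, 2(c), is redacted after its opening words.

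Section 6.4.1 has three clauses that bear on this:

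- For laboratory parameters or assessments that fail at first, "a single retest within the 28 day screening period is permitted".
- Items listed in Table 2-1 "may be repeated in an effort to find all possible well-qualified participants", with no number given. CLASI is listed in Table 2-1.
- "The most current result prior to randomization is the value by which study inclusion will be assessed".

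The section also asks for a complete new Screening Visit at rescreening, then says that some assessments may not need repeating. Table 2-1, footnote b, adds: "Screening procedures should be performed within the 28 day window prior to Day 1". Section 6 closes the exception route: "Prospective approval of protocol deviations to recruitment and enrollment criteria, also known as protocol waivers or exemptions, is not permitted".

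**The concern.** A rule that needs two values meets a rule that uses one. The Day 1 CLASI-A is always obtained before randomization, so if the last sentence of Section 6.4.1 is applied to it, Day 1 is always the most current result and the Screening half of the requirement does nothing. Someone scoring 6 at Screening and 9 on Day 1 would be eligible on that reading and an eligibility deviation on the other, with no waiver available. Sites could differ.

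The score also matters more than most screening tests. CLASI-A is both the entry gate and the basis of the primary endpoint, percent change from baseline at Week 16. A looser gate lets in more people whose usual score is below 8 and who happened to score high on Day 1. Their scores drift back down without any treatment, which adds noise and an untreated fall. There is also a plain mismatch inside the section, between one retest and repeats with no limit.

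**Working it through.** **Step 1. Set the readings side by side.** Strict: the first Screening score and Day 1 must both reach 8. Reading (a): a retest in the Screening Period may replace the failed score, and Day 1 must still reach 8. Reading (b): only the latest score before randomization, Day 1, must reach 8.

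| First Screening / retest / Day 1 | Strict | (a) | (b) |
|---|---|---|---|
| 6 / none / 9 | out | out | in |
| 6 / 9 / 9 | out | in | in |
| 6 / 7 / 9 | out | out | in |
| 9 / none / 9 | in | in | in |
| 9 / none / 7 | out | out | out |
| 6 / 9 / 7 | out | out | out |

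The readings part only when the first Screening score is below 8 and Day 1 is at least 8.

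**Step 2. Which reading fits the text?** The heading of Section 6.4.1 confines it to retesting in the Screening Period, and its repeat clause points to Table 2-1. The Day 1 CLASI belongs to Table 2-2, as a separately scheduled efficacy assessment. It is not a repeat of the Screening one. The most-current-result sentence therefore selects among repeats of the same scheduled test. Reading (b) would empty a requirement that the Synopsis and Section 5.1.2 state expressly; reading (a) leaves every sentence with something to do.

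**Step 3. Rescreening.** It starts after the initial four-week Screening Period has ended. Footnote b puts screening procedures within 28 days before Day 1. A CLASI from an earlier attempt is therefore normally out of window, apart from the approved 7-day extension. The remark about not repeating everything fits items with longer validity, such as the chest X-ray, which may be up to 6 months old.

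**Step 4. Chance of qualifying, one attempt, usual score 6.** The documents give no visit-to-visit SD, so 2 points is assumed (range 1.5 to 3), with independent visits and a cut at 7.5 for whole-number scores. Per visit, p = P(Z > 1.5/SD) = 0.159, 0.227, 0.309 for SD 1.5, 2, 3.

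- Strict: p² = 0.025, 0.051, 0.095.
- (a): p × (1 − (1 − p)²) = 0.046, 0.091, 0.161.
- (b): p itself.

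**Step 5. Effect on the trial.** This is a simulation under further assumptions: usual score log-normal, median 10, log-SD 0.5; visit SD 2; true fall 20% on placebo and 45% on active; patient SD 35 points; 25 per arm; every failed Screening score retested under (a) or carried to Day 1 under (b).

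| | Strict | (a) | (b) |
|---|---|---|---|
| Untreated change, no rescreening | −0.9% | −1.7% | −3.0% |
| Untreated change, up to two rescreens | −2.6% | −3.6% | −5.6% |
| Power, no rescreening | 58.3% | 57.3% | 56.3% |
| Power, up to two rescreens | 56.3% | 55.8% | 53.8% |
| Screens per randomized, no rescreening | 1.61 | 1.50 | 1.41 |

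Against the strict rule, (a) adds 1.7 − 0.9 = 0.8 points of untreated fall without rescreening and 3.6 − 2.6 = 1.0 with it. It costs 58.3 − 57.3 = 1.0 and 56.3 − 55.8 = 0.5 points of power. The power loss is a little larger at visit SD 3.

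**Step 6. These are ceilings.** Without rescreening, 7.1% of those randomized under (a) had a first Screening score below 8. If only a quarter of failed scores were retested, that drops to 1.9%. With rescreening, the strict rule itself admits 9.8% whose very first Screening score was below 8, against 13.7% under (a), so the retest adds 13.7 − 9.8 = 3.9 points.

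**The case for a change.** The best case for a change is that reading (a) is an inference. No visible sentence exempts CLASI from Section 6.4.1 or says which rule prevails. Consultation with the medical monitor is optional and concerns whether a repeat is clinically relevant, not which score counts. With waivers barred, a wrong reading at a site becomes a deviation, and two sentences would prevent it.

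Part of this stands. The retest limit is worded inconsistently, and the precedence is left to the reader. But criterion 2(c) is blacked out exactly where the CLASI rule would stand, so the visible text cannot show that the plan is silent. The remedy that would change something, barring any CLASI retest, has a price: 75 × (1.61 − 1.50) ≈ 8 more people screened than under (a) (range 4 to 13 over the assumed inputs) in what the sponsor calls a rare disease population. Allowing one retest is a fair trade for that. The milder remedy only writes down what a sensible reader already does.

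**Conclusion.** No change follows. The two-visit rule and the retest rule can both be obeyed, and the remaining mismatch on the number of retests is a slip of wording.

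The results stay sound on either reading. Eligibility is settled before randomization, so any looser entry is shared by all arms and does not bias the comparison. Section 10.3.1 analyses efficacy in the randomized population, and Section 10.2 defines no per-protocol set, so a disputed Screening score would not remove anyone from the primary analysis. Section 5.4 gives the purpose as estimating the effect, and the p-values are nominal, so a power difference of about 1 point decides nothing. That figure is for a single dose against placebo; the planned contrast of both doses combined, about 50 against 25, has more participants behind it.

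Even the strained reading (b) costs at most 45.1 − 41.4 = 3.7 points of power, at visit SD 3 with rescreening. All these sizes rest on assumed score distributions, visit SD, effects and full uptake of retesting; none comes from the documents. The reading of the text does not depend on them, but it is subject to what the redacted criterion says.

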7 TREATMENT

Study treatment is defined as any investigational treatment(s), marketed product(s), placebo or medical device intended to be administered to a study participant according to the study randomization or treatment allocation.

Study treatment includes both Investigational [Medicinal] Product (IP/IMP) and Non-investigational- [Medicinal] Product (Non-IP/Non-IMP) and can consist of the following: deucravacitinib, background medications, and placebo. Information about the pharmacology and previous experience with deucravacitinib is provided in [Section 3.2](#).

An investigational product, also known as investigational medicinal product in some regions, is defined a pharmaceutical form of an active substance or placebo being tested or used as a reference in a clinical study, including products already with a marketing authorization but used or assembled (formulated or packaged) differently than the authorized form, or used for an unauthorized indication, or when used to gain further information about the authorized form.

Other medications used as support or escape medication for preventative, diagnostic, or therapeutic reasons, as components of the standard of care for a given diagnosis, may be considered as non-investigational products.

Study treatment descriptions including dosage form, potency, IP/non-IMP, and storage conditions are presented in [Table 7-1](#).

Table 7-1: Study Treatments for IM011132

Product Description / Class and Dosage Form	Potency	IP/Non-IMP	Blinded or Open Label	Packaging / Appearance	Storage Conditions (per label)
Deucravacitinib Oral Tablet	3 mg or 6 mg	IP	Blinded		Store 15 to 25°C; Protect from light; Store in original container.
Deucravacitinib-matching Placebo Oral Tablet	Not applicable	IP	Blinded		Store 15 to 25°C; Protect from light; Store in original container.

Note: Background therapies will be obtained as per participant's local standard of care.

7.1 Treatments Administered

[figure not shown]
The selection and timing of dose for each participant are presented in Table 7.1-1.

Table 7.1-1: Selection and Timing of Dose

Study Treatment	Unit dose strength(s) / Dosage level(s)	Dosage formulation Frequency of Administration	Route of Administration
Deucravacitinib (3 mg tablet)	3 mg BID	1 active and 1 placebo tablet in the morning and 1 active and 1 placebo tablet in the evening.	Oral
Deucravacitinib (6 mg tablet)	6 mg BID	1 active and 1 placebo tablet in the morning and 1 active and 1 placebo tablet in the evening.	Oral
Deucravacitinib-matching Placebo (oral tablet)	BID	2 placebo tablets in the morning and 2 placebo tablets in the evening.	Oral

Abbreviation: BID = twice a day.

Blinded study treatment will be supplied [REDACTED] at each study visit. The tablets will be arranged into sets to be taken in the morning and in the evening, approximately 12 hours apart. The participant should be instructed to take 2 tablets in the morning and 2 tablets in the evening. Study treatment may be taken with or without food. If a scheduled dose of study drug is missed and the participant remembers within 4 hours of the scheduled dose time, the dose should be taken as soon as possible. If the missed dose is remembered later than 4 hours after the scheduled dose time, the dose should be skipped and the next dose taken at the appropriate time. Any missed doses should be returned at the next study visit.

7.2 Method of Treatment Assignment

At the time of the Screening Visit, immediately after informed consent is obtained and before any study-related procedures are performed, the investigative site will access the enrollment option utilizing Interactive Response Technology (IRT) for assignment of a participant number (including participants not subsequently randomized or treated). This number will be unique across all sites. Enrolled participants, including those not dosed, will be assigned sequential participant numbers. The participant number may not be used for any other participant. If a potential participant is rescreened, they will be given a new identification number.

Eligible participants will be centrally randomized using IRT to receive oral treatment with deucravacitinib 3 mg BID, 6 mg BID, or deucravacitinib-matching Placebo BID in accordance with stratification criteria (see [Section 5.1](#)). At the Week 16 study visit, the participants initially

assigned to receive Placebo and who agree to continue study participation will be re-randomized by the IRT to receive oral treatment with either deucravacitinib 3 mg BID or 6 mg BID until Week 52. Re-randomized participants will receive a new randomization number prior to dosing.

Before the study is initiated, each user (at investigative sites) will receive log-in information and directions on how to access the IRT. Treatment codes will be assigned prior to dosing.

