5.1.3 Active Treatment Period (Week 16 to Week 52)

Participants who complete the placebo-controlled treatment period will continue into an active treatment period for an additional 36 weeks of treatment.

At Week 16, participants receiving placebo during the placebo-controlled treatment period will be re-randomized 1:1 in a blinded-fashion to receive active treatment with either deucravacitinib 3 mg BID or 6 mg BID until Week 52. Participants receiving deucravacitinib 3 mg BID or 6 mg BID through Week 16 will continue on the originally randomized treatment in a blinded manner through Week 52 (Table 2-3).

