7.3 Blinding

This is a randomized, double-blind, placebo-controlled study. During the placebo-controlled period and the active treatment period, the IP will remain blinded, to prevent study personnel and participants from knowing the IP assignment. For the [REDACTED] database lock, BMS personnel who have access to the unblinded data are not to discuss or make materials available that would unblind individual participant data to the personnel involved in the study conduct [REDACTED]. A separate blinding charter will detail the unblinding process. Access to treatment codes will be restricted from all participants and site personnel prior to final database lock, with exceptions as specified below.

Blinding of treatment assignment is critical to the integrity of this clinical study. However, in the event of a medical emergency or pregnancy in an individual participant in which knowledge of the investigational product is critical to the participant's management, the blind for that participant may be broken by the investigator. The participant's safety takes priority over any other considerations in determining if a treatment assignment should be unblinded.

Before breaking the blind of an individual participant's treatment, the investigator should determine that the unblinded information is necessary, ie, that it will alter the participant's immediate management. In many cases, particularly when the emergency is clearly not related to the investigational product, the problem may be properly managed by assuming that the participant is receiving active product. It is highly desirable that the decision to unblind treatment assignment be discussed with the Clinical Trial Physician/Medical Monitor, but the investigator always has ultimate authority for the decision to unblind. The actual TASK of unblinding can be delegated by the investigator to a designee assigned the task on the Delegation of Authority. The Principal Investigator or appointed designee should access IRT for emergency unblinding AFTER the decision to unblind the participant has been documented.

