9.1 Efficacy Assessments

Protocol-specific training and assessments must be successfully completed so that investigators or designees can be qualified to perform assessments using the CLASI, [REDACTED] [REDACTED]. Every effort must be made to ensure that the same evaluator(s) complete the assessment for each participant. If the evaluator(s) is unable to complete the evaluation, then a qualified individual with overlapping experience may perform the evaluation. Documentation of who performed the evaluation is to be recorded in source documents. Assessments are to be performed at approximately the same time of day throughout the duration of the study.

[figure not shown]
The following sections describe the procedures or tools to be used to assess participants' SLE disease activity during the study (also refer to the Schedule of Activities in [Section 2](#)).

9.1.1 ***Cutaneous Lupus Erythematosus Disease Area and Severity Index (CLASI)***

Refer to [Appendix 8](#). The CLASI is a validated scale used to assess cutaneous manifestations of SLE consisting of 2 scores. The first (CLASI-A) summarizes the activity of the disease while the second is a measure of the damage done by the disease. Activity is scored on the basis of erythema, scale/hyperkeratosis, mucous membrane involvement, acute hair loss, and nonscarring alopecia. CLASI-A will be the key efficacy assessment to provide clinical evidence of response to deucravacitinib in the active DLE/SCLE population. The second scale (CLASI-D) assesses damage and is scored in terms of dyspigmentation and scarring, including scarring alopecia. Literature suggests that a 4-point or 20% decrease in the CLASI-A score from baseline is considered an improvement in disease activity.³²

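### Does giving a new randomization number at Week 16 only to former placebo participants break the blind?

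*Combined protocol and SAP*

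**What the plan says.** Section 7.2 states that at Week 16 the participants initially "assigned to receive Placebo and who agree to continue study participation will be re-randomized by the IRT" to one of the two active doses. It adds: "Re-randomized participants will receive a new randomization number prior to dosing". Section 5.1.3 describes the same step as participants being "re-randomized 1:1 in a blinded-fashion to receive active treatment with either deucravacitinib 3 mg BID or 6 mg BID until Week 52", while those already on active drug stay on their original dose, also blinded. The note in Table 2-2 reads: "Only participants on placebo will be re-randomized, but IRT will be contacted for all participants to maintain the blind".

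Section 7.3 keeps the investigational product blinded in both treatment periods and says: "Access to treatment codes will be restricted from all participants and site personnel prior to final database lock", apart from listed exceptions. It refers to a separate blinding charter and an IRT manual; neither is supplied, and parts of the section are redacted.

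On visit order, Table 2-2 says for Day 1: "Confirm eligibility criteria and complete Baseline assessments prior to randomization". Section 5.1.2 says the same of the entry score: "CLASI-A assessment must be performed for eligibility at Screening and Baseline (Day 1) prior to randomization". No equivalent order is given for the Week 16 CLASI and the Week 16 IRT contact. Section 9.1 asks for rater continuity: "Every effort must be made to ensure that the same evaluator(s) complete the assessment for each participant".

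**The concern.** Contacting the IRT for everyone hides the fact that a re-randomization took place. It does not by itself hide what the transaction returns. If former placebo participants come away with a new number, the others do not, and staff can see the difference, then prior arm is known for every continuing participant. Section 7.3 restricts treatment codes and does not mention randomization numbers, so it does not plainly cover the number.

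CLASI-A is rated by an investigator or designee, usually the same person throughout, and the investigator also judges whether adverse events are related to treatment. A rater who knew that a participant had just left placebo might expect improvement. If the Week 16 CLASI were scored after the IRT contact, the primary rating itself could be made with prior arm known. Scores can be low: at the entry minimum of 8, one CLASI-A point is 1/8 = 12.5 percentage points on that participant's percent change. That shows how sensitive one participant's value is; it does not estimate bias.

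**Working it through.** The plan gives no figure on this point, so the check asks what the number could reveal, to whom, and which results it could reach.

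**What a visible number would reveal.** Inputs: about 75 participants randomized 1:1:1 (Section 5.2), so 75/3 = 25 per arm and a prior probability of placebo of 1/3. Assume equal continuation across arms. Write P for the probability that a continuing participant was on placebo.

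- Number issued only to former placebo participants, and visible: P given a new number = (1/3 × 1) / (1/3 × 1 + 2/3 × 0) = 1. P given no new number = 0.
- Number issued to all continuing participants: P = (1/3 × 1) / (1/3 × 1 + 2/3 × 1) = 1/3, so nothing is learned.
- Number not displayed to blinded staff: P stays at 1/3.

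In no case does the number show the current dose, 3 mg or 6 mg.

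**How many participants and ratings.** The documents give no early-stopping rate, so 0%, 10% and 20% are assumed, equal across arms. Table 2-3 has on-treatment CLASI ratings at Weeks 20, 24, 28, 40 and 52, which is five visits. The products are upper bounds, with no further loss after Week 16.

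| Stopping before Week 16 | Former placebo | Originally active | Total | Ratings, Weeks 20 to 52 |
|---|---|---|---|---|
| 0% | 25 | 50 | 75 | 5 × 75 = 375 |
| 10% | 22.5 | 45 | 67.5 | 5 × 67.5 = 337.5 |
| 20% | 20 | 40 | 60 | 5 × 60 = 300 |

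Table 2-3 also has a CLASI at Week 56, the safety follow-up 28 days after the last dose. Including it gives 6 × 60 = 360 to 6 × 75 = 450.

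**Which results those ratings feed.** In Table 4-1 the visible primary and secondary efficacy objectives are set at Week 16. Section 10.3.1 gives nominal p-values at Week 16 only. The safety summary in Section 10.3.2 covers the 16-week placebo-controlled period. After Week 16 every continuing participant is known to be on active drug and no placebo arm remains. The later ratings therefore bear on description of durability by treatment sequence, not on a visible placebo comparison.

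**What must hold for the primary rating to be exposed.** All three of these: the number is visible at the site; the person scoring CLASI sees it; and CLASI is scored after the IRT contact. Then up to 60 to 75 Week 16 ratings are affected; if any one fails, none are. The documents establish none of the three. On the third, Section 5.1.3 moves participants forward once they complete the placebo-controlled period, which suggests that Week 16 assessments come first. The Day 1 order exists because the baseline score decides eligibility; no CLASI threshold is visible for re-randomization at Week 16.

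**The case for a change.** The best case for a change is that the sponsor saw this leak and closed only half of it. The IRT contact for all participants disguises the transaction but not its output. Calling the step blinded states an aim rather than a mechanism. Section 7.2 uses randomization number and treatment code as separate terms, so restricting codes in Section 7.3 need not protect numbers. Site users hold IRT log-ins, and drug is dispensed at the same visit, so a site could plausibly see the number. Section 8.1 makes unblinding for any reason a ground for stopping study drug, and Section 5.4 justifies the 52 weeks by durability and one-year safety, so later ratings have value. A clarifying sentence would be short.

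Much of this stands. The text is silent, and a visible placebo-only number would identify prior arm with certainty. But silence about a display setting is not evidence of a leak. That the others receive no number is itself inferred: no text denies them one. An IRT that showed sites a placebo-only number would contravene requirements already in Sections 5.1.3 and 7.3 and the purpose stated in Table 2-2. Section 7.3 also treats sponsor staff who obtain the randomization codes as unblinded, so allocation information is already handled as unblinding material. The sentence would add implementation detail to an existing rule, and under Appendix 2 a protocol amendment needs ethics committee approval. Fixing the Week 16 order in writing would be good practice, but its absence is not an error.

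**Conclusion.** No change to the plan is needed. This is a gap in operational detail that the people building and testing the IRT would be expected to fill in line with the blinding requirements the protocol already sets. If those requirements are followed, the number is concealed or issued to all, and the effect is nil.

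If they were not, prior arm would be known for about 60 to 75 continuing participants, with at most about 300 to 375 on-treatment ratings affected, under the assumption of 0% to 20% stopping before Week 16 equally across arms. Those ratings feed no visible primary, secondary or placebo-controlled comparison, and current dose would stay masked. The primary endpoint is reached only if the three conditions above all hold.

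The conclusion rests on the visible text. The IRT manual and blinding charter are not supplied, and some endpoints and parts of Section 7.3 are redacted. A check of the IRT display settings would settle the matter without touching the protocol.
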